Facility Director for Main Site

[name]

Email: [contact]

Phone:

Study Details

Describe the purpose of the investigation. If this is a clinical trial, this should include a description of the disease and the goals of the research.

Chronic pain is a significant public health concern in the U.S., for which prescription opioids have historically been the standard treatment. This has resulted in striking rates of opioid use disorders and fatal overdoses. Identifying non-opioid medications for the management of chronic pain with minimal abuse liability is a public health necessity, and cannabinoids are a promising drug class for this purpose. More than 80% of medicinal cannabis users report pain as their primary medical indication. These patients tend to seek products that are low in delta-9-tetrahydrocannabinol (THC; the primary psychoactive, and thus intoxicating, component of cannabis), and high in cannabidiol (CBD), a cannabinoid that purportedly has therapeutic benefit for pain but does not produce intoxicating effects [1]. However, there are few well-controlled human laboratory studies assessing the efficacy of high-CBD cannabis for pain in the context of abuse, and even less is known regarding the effects of daily repeated use of cannabis on pain and its relationship to abuse liability. Carefully controlled research is needed. The proposed randomized, within-subjects, placebo-controlled 16-day crossover inpatient human laboratory pilot study (N = 16 healthy cannabis users; 8 men, 8 women) will address three important gaps in our understanding of the potential therapeutic utility of cannabis for pain: 1) If abruptly switching active cannabis (4.91% CBD/2.98% THC) to inactive cannabis (0% CBD/THC) increases experimental pain sensitivity, i.e. hyperalgesia, relative to baseline and if these effects parallel measures of cannabis withdrawal such as disrupted mood and sleep (Each cigarette contains approximately 39.28mg of CBD and 23.84mg of THC. They smoke 75% of one cigarette, so each dose is approximately 29.46mg of CBD and 17.88mg of THC); 2) If tolerance to the analgesic and abuse-related effects of cannabis is reversed following 7 days of abstinence from active-THC cannabis (by administering 0% CBD/THC, inactive cannabis); 3) If tolerance is present/develops to repeated, daily smoked cannabis (4.91% CBD/2.98% THC) administration on measures of experimental pain and abuse liability. Two distinct modalities of experimental pain will be assessed: The Cold Pressor Test (CPT) and Quantitative Sensory Testing Thermal Temporal Summation (QST-TTS). The study will start with a day of active cannabis administration (4.91% CBD/2.98% THC) given 3x/day in order to standardize cannabis exposure across participants (Day 1), and will be followed by a 7-day "inactive phase" (Day 2-8) in which participants will smoke inactive cannabis (0% CBD/THC) 3x/day during this 7-day period. The last 7 days (Day 9-15) will comprise an "active cannabis phase" in which participants will smoke cannabis (4.91% CBD/2.98% THC) 3x/day. Throughout the study, experimental pain and abuse-related effects will be assessed, as will sleep and subjective mood assessments. With rates of chronic pain increasing and limited availability of safe and effective treatment alternatives to opioids, this study will provide essential data regarding the efficacy of daily cannabis use on measures of analgesia and abuse liability and the consequences of cannabis abstinence on measures of pain, as it is possible that abrupt cessation of cannabis use will lead to worsened baseline pain.

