
General Overview:

This within-subjects study will examine the effects of daily repeated use of cannabis on pain and its relationship to abuse liability. Healthy, non-treatment seeking cannabis smokers (N=16, 8M, 8F) will be admitted to the research center on 5- South of NYSPI for a 16-day inpatient stay. On the first full inpatient day, participants will smoke active cannabis (4.91% CBD/2.98% THC). Days 2-8 will comprise the Inactive Phase, in which placebo cannabis (0% CBD/THC) will be administered 3x/day. The next 7 days (Day 9-15) will be the Active Phase, in which active cannabis (4.91% CBD/2.98% THC) will be administered at the same time points (Table 1). Participants will complete subjective effects visual analog scales and a cannabis rating form daily, and will complete the Cold-Pressor Test and Quantitative Sensory Testing-Thermal Temporal Summation on Days 1, 2, 5, 8, 9, 12, and 15 to explore three critical questions regarding cannabis' therapeutic utility for pain (as illustrated in Figure 1): 1) If abruptly switching active cannabis to inactive cannabis increases experimental pain sensitivity, i.e. hyperalgesia (Day 2-8; red bars) relative to baseline and if these effects parallel measures of cannabis withdrawal such as disrupted mood and sleep; 2) If pharmacological tolerance to the analgesic and abuse-related effects of cannabis is reversed following 7 days of abstinence from active-THC cannabis (by administering 0% CBD/THC, inactive cannabis): defined as a) a significant decrease in CPT latencies and QST-TTS response following active cannabis administration on Day 12 or Day 15 compared to Day 9 (Active Phase), and b) a significant decrease in subjective visual analog scale ratings of abuse, i.e. 'Good Drug Effect' following active cannabis administration on Day 12 or Day 15 (Active Phase) compared to Day 9 (Active Phase); 3) If tolerance is present/develops to repeated, daily smoked cannabis (4.91% CBD/2.98% THC) administration on measures of experimental pain and abuse liability (green bar): defined as a significant increase in CPT latencies and QST-TTS response and 'good drug effect' after active cannabis administration when Day 9 of the Active Phase is compared to Day 1.

Provide the hypothesis for this research.

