Aim 1. Determine the effects of abstinence from active cannabis (by use of 0% THC cannabis) on experimental pain. We hypothesize that (a) abrupt abstinence will result in increased CPT and QST-TTS responses, indicative of withdrawal-induced hyperalgesia.

Aim 2. Determine if a) tolerance is present (Day 1) and is reversed following abstinence from active cannabis (Days 2-8); b) tolerance develops to daily smoked active cannabis (4.91% CBD/2.98% THC; Days 9-15) administration on pain and abuse liability measures. We hypothesize that: (a) existing analgesic tolerance will be reversed following abstinence from active cannabis; (b) over the course of the active cannabis phase, tolerance will develop to cannabis' analgesic but not abuse-related effects.

Include pertinent information about the relationship of the proposed research to previous studies and describe the significance of the proposed research. Be brief.

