Since we will recruit moderate-heavy cannabis users with varied use patterns, they will enter the study with varying pharmacological tolerance. Therefore, Study Day 1 will be an initial day of active cannabis administration to standardize exposure to the same strength of smoked cannabis across participants prior to enforced abstinence from active cannabis in the Inactive Phase (Day 2-8). Participants will be administered active cannabis (two one 4.91% CBD/2.98% THC cigarettes) at 1000h, 1300h, and 1600h.

Days 2-8 (Inactive Phase)

On Study Days 2-8, participants will be administered one inactive cannabis cigarette (0.00% CBD/THC) at the same three time-points (1000, 1300, 1600). We have shown that inactive cannabis controls for expectancy effects of smoking, producing small but reliable increases in ratings of 'high' [5]. Therefore, this phase will assess how abstinence from active- THC cannabis affects pain outcomes in parallel to measures of cannabis intoxication and withdrawal (mood, sleep).

Days 9-15 (Active Phase)

On Study Days 9-15 participants will be administered an active cannabis cigarette (one 4.91% CBD/2.98% THC cigarette) at the same three time-points (1000, 1300, 1600), with the exception of Day 15 where they will be administered active cannabis only at 1000. This phase will allow us to see if CPT and QST pain outcomes and abuse liability change over time

Move Out

Following completion of all assessments of Day 15, the PI will discuss with the participants benefits of cannabis cessation, highlighting availability of a range of treatment options, prior to discharge. At 180 minutes post-cannabis administration, participants will complete field sobriety tests, vital signs, and a Mini-Mental State Exam (MMSE), and will be permitted to leave once they meet discharge criteria. Criteria for discharge will be met when participants report no ongoing subjective drug effects and have no signs of impairment or intoxication, pass the field sobriety test, have normal vitals, and a normal mental status score as assessed by the MMSE. [name], [name], or [name] will make the final determination that the patient is sober and medically stable and can leave the facility.

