Provide the IND number.

36369

Name the person/entity that holds/is the Sponsor of the IND.

If the IND holder is an OMH investigator, please contact the IRB for information on responsibilities of Sponsor-Investigators.

[name].

Please attach any correspondence from the FDA with your submission.

IND Ownership Transfer to [name] 2023 FDA Correspondence

RWF IND 036369 updates_8016_9.26.22.pdf FDA Correspondence

rwf IND Form of Notice_8016.pdf FDA Correspondence

RWF IND_1571+PSF_add 8016_6.8.22.pdf FDA Correspondence

Subjects

Target Enrollment:

This refers to the target subjects enrollment, i.e., the number of subjects necessary to complete research objectives.

20

Total number of subjects requested to reach target enrollment:

This refers to the estimated number of subjects you must "over-enroll" to meet your target enrollment either by active screening or review of records for eligibility.

24

Please identify the groups of the study and how many subjects will be enrolled in each group.

Click "save" at the end of each row.

If you have multiple groups, please use the number (#) assigned to each group on the left of this table to indicate that group in the inclusion/exclusion criteria table (to specify which inclusion/exclusion criteria belong to which subject group).

Numbers here should equate to the number entered for Target Enrollment.

#	Subject Group	Subject Number
1	Healthy, non-treatment seeking heavy cannabis smokers	20

Please provide a justification for your sample size.

Power calculations were performed using G*Power, with the following assumptions: significance level of $\alpha = 0.05$, effect size (Cohen's d) of 0.7, and within-subjects correlations of 0.6 for repeated measures. Based on our residential laboratory studies in cannabis smokers, we estimate that 4 of the 24 participants may drop out. The large within-subject correlations (typically ranging from 0.60-0.95) between conditions (active cannabis vs. inactive cannabis) allow for sufficient statistical power with $n=20$ completers.

Inclusion & Exclusion:

Give detailed inclusion and exclusion criteria (per group, if you have multiple groups). Note that order does not indicate importance. Click **Save** at the end of each row to both save data and to add a new row. For the final row, click **Save** and leave the new row blank.

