All data analyses will be based on models using repeated measures analysis of variance (RM-ANOVA) analyzed as a function of cannabis condition (active vs. inactive) and day (Day 1-15), and sets of planned comparisons, calculated with SPSS or SUPERANOVA statistical packages. The planned comparisons, outlined below, are a priori, and designed to test the specific hypothesis for each aim. Tests of differences for all comparisons will be based on F-statistics with degrees of freedom corrected, depending on the observed within-subject correlation of the measures, using the method of Geiser and Greenhouse or Huynh and Feldt. Results will be considered statistically significant at $p < 0.05$, using 2-tailed tests. Distribution of demographic variables (ethnicity, age, sex) will be described in terms of means, standard deviations, proportions, and 95% confidence intervals, where appropriate.

Please list all references.

1. Nahin, R.L., *Estimates of pain prevalence and severity in adults: United States, 2012*. *J Pain*, 2015. **16**(8): p. 769-80.
2. Dowell, D., T.M. Haegerich, and R. Chou, *CDC guideline for prescribing opioids for chronic pain—United States, 2016*. *Jama*, 2016. **315**(15): p. 1624-1645.
3. LeResche, L., K. Saunders, S. Dublin, S. Thielke, J.O. Merrill, S.M. Shortreed, C. Campbell, and M.R. Von Korff, *Sex and age differences in global pain status among patients using opioids long term for chronic noncancer pain*. *Journal of women's health*, 2015. **24**(8): p. 629-635.
4. Wasserman, R.A., C.M. Brummett, J. Goesling, A. Tsodikov, and A.L. Hassett, *Characteristics of chronic pain patients who take opioids and persistently report high pain intensity*. *Regional anesthesia and pain medicine*, 2014. **39**(1): p. 13.
5. Chou, R., J.A. Turner, E.B. Devine, R.N. Hansen, S.D. Sullivan, I. Blazina, T. Dana, C. Bougatsos, and R.A. Deyo, *The effectiveness and risks of long-term opioid therapy for chronic pain: a systematic review for a National Institutes of Health Pathways to Prevention Workshop*. *Annals of internal medicine*, 2015. **162**(4): p. 276-286.
6. Dunn, K.M., K.W. Saunders, C.M. Rutter, C.J. Banta-Green, J.O. Merrill, M.D. Sullivan, C.M. Weisner, M.J. Silverberg, C.I. Campbell, B.M. Psaty, and M. Von Korff, *Opioid prescriptions for chronic pain and overdose: A cohort study*. *Annals of Internal Medicine*, 2010. **152**(2): p. 85-92.
7. Statistics, N.C.f.H., *Mortality Data for 2017*. 2018.

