Title: Repeated Cannabis Administration on Experimental Pain and Abuse Liability

NCT: 04576507

Document date: April 14, 2025

Statistical Analysis

Overview: All data analyses will be based on models using repeated measures analysis of variance (RM-ANOVA) analyzed as a function of cannabis condition (active vs. inactive) and day (Day 1-15), and sets of planned comparisons, calculated with SPSS or SUPERANOVA statistical packages. The planned comparisons are *a priori*, and designed to test the specific hypothesis for each aim. Tests of differences for all comparisons will be based on F-statistics with degrees of freedom corrected, depending on the observed within-subject correlation of the measures, using the method of Geiser and Greenhouse or Huynh and Feldt. Results will be considered statistically significant at $p < 0.05$, using 2-tailed tests. Distribution of demographic variables (ethnicity, age, sex) will be described in terms of means, standard deviations, proportions, and 95% confidence intervals, where appropriate.

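### Condition is fixed by study day, so it adds 0 df to the SAP's condition-and-day model; the Aim 2 day pairs are missing from both analysis sections and carry crossed labels, and nothing supports the label randomized crossover

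*SAP*

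**What the plan says.** **Model.** The SAP (Statistical Analysis, Overview) and the protocol (Statistical/Data Analysis Plan) give the same repeated-measures ANOVA, "analyzed as a function of cannabis condition (active vs. inactive) and day (Day 1-15), and sets of planned comparisons". The protocol adds "The planned comparisons, outlined below, are a priori, and designed to test the specific hypothesis for each aim", but the reference list comes next. The SAP drops the pointer and lists no comparisons either.

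**Design.** Study Details calls this "The proposed randomized, within-subjects, placebo-controlled 16-day crossover inpatient human laboratory pilot study". The Subjects table has a single group, "Healthy, non-treatment seeking heavy cannabis smokers". The day-by-day procedures give everyone active cannabis on Day 1. Then: "On Study Days 2-8, participants will be administered one inactive cannabis cigarette (0.00% CBD/THC) at the same three time-points". Active cannabis follows on Days 9-15. No section gives a second sequence, an allocation ratio or a randomization method. The Risks text on cannabis administration speaks of either an active or a placebo condition during the active phase, which conflicts with the Days 9-15 procedures.

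**Aims.** For Aim 1 the General Overview gives only "hyperalgesia (Day 2-8; red bars) relative to baseline and if these effects parallel measures of cannabis withdrawal". It defines reversal of tolerance as a fall on Day 12 or Day 15 compared with Day 9, and presence or development of tolerance as a rise "when Day 9 of the Active Phase is compared to Day 1". The hypothesis section differs. Aim 2(a) asks whether "tolerance is present (Day 1) and is reversed following abstinence from active cannabis (Days 2-8"), and Aim 2(b) concerns development over Days 9-15.

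**The concern.** A model with condition and day as separate factors suggests that active versus inactive cannabis can be tested apart from time. With one fixed order it cannot. The questions the trial asks are contrasts between particular days, and a reader of the SAP cannot tell which contrasts will be tested or what each would show.

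Three things are at stake. First, the same numerical result could be reported under different names, because the Overview and Aim 2 attach reversal and development to different day pairs. Second, the protocol says the study is now at the data-analysis stage, so whatever remains open could be settled with data in hand. Third, the words randomized and crossover suggest a protection against time effects that the described schedule does not provide.

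**Working it through.** The documents state no degrees of freedom for this model, so there is no figure of theirs to reproduce. The sample size does not bear on the point.

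**1. Degrees of freedom.** Inputs are the day-to-condition map above and the pain-test days 1, 2, 5, 8, 9, 12 and 15. The indicator for active cannabis equals the sum of the day indicators for Day 1 and Days 9-15, so it already lies in the space spanned by day.

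- Days 1-15: 15 of 30 condition-by-day cells exist. Rank with day, plus condition, plus interaction: 15, 15, 15.
- Pain days: 7 of 14 cells exist. Rank: 7, 7, 7.
- Partition of day on pain days: 6 = 1 (active vs inactive) + 3 (among four active days) + 2 (among three inactive days). Over Days 1-15: 14 = 1 + 7 + 6.

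**2. Other codings.** With day as a linear trend, rank goes from 2 to 3, so condition is estimable. It still correlates with day: 0.65 over 15 days, 0.44 on pain days. With day-within-phase and Day 1 dropped (2, 5, 8 against 9, 12, 15), phase day plus condition has rank 4. Adding linear study day leaves it at 4, so condition cannot be separated from linear time. Neither analysis section states either coding.

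**3. Contrasts the aims need.** Day 9 - Day 1, Day 12 - Day 9 and Day 15 - Day 9 use 3 df. If Day 1 is the Aim 1 reference, Days 2, 5 and 8 each against Day 1 use the other 3 of the 6. All are estimable. The pooled contrast puts weight 1/4 on each active pain day and -1/3 on each inactive one. Its product with Day 9 - Day 1 is 1/4 - 1/4 = 0, and likewise for the other two Aim 2 pairs, so a pooled test says nothing about Aim 2.

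**4. Labels.** For CPT latency, where longer means more analgesia:

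- A larger effect on Day 9 than on Day 1 means that tolerance was present on Day 1 and abstinence undid it. Aim 2(a) calls this reversal; the Overview calls it present or developing tolerance.
- A smaller effect on Day 12 or 15 than on Day 9 means tolerance built up under daily use. Aim 2(b) calls this development; the Overview calls it reversal.

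**5. Direction.** The Overview requires CPT latency and QST-TTS response to move the same way. The Experimental Assessments section expects cannabis to lower QST-TTS response, and Aim 1 reads a raised response as hyperalgesia. Taken literally, loss of analgesia would raise QST-TTS response and fail the Overview's definition.

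**6. Time and test exposure.** The CPT and QST-TTS section gives 1 + 6 = 7 tests per pain day; Repeated Pain Challenges gives 8. Training is not counted.

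| Contrast | Days apart | Extra prior tests at 7/day | At 8/day |
|---|---|---|---|
| Day 9 vs Day 1 | 8 | 4 × 7 = 28 | 4 × 8 = 32 |
| Day 12 vs Day 9 | 3 | 7 | 8 |
| Day 15 vs Day 9 | 6 | 14 | 16 |
| Mean of Days 2, 5, 8 vs Day 1 | 5 - 1 = 4 | (7 + 14 + 21)/3 = 14 | (8 + 16 + 24)/3 = 16 |
| Pooled active vs inactive | 9.25 - 5 = 4.25 | 26.25 - 14 = 12.25 | 30 - 16 = 14 |

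Day 9 vs Day 1, which carries Aim 2(a), is the most exposed. The documents give no drift rate, so these are exposures and not biases.

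**The case against.** - **The redundancy blocks no aim.** The SAP provides for planned comparisons, and the General Overview gives the Aim 2 day pairs with directions. This stands. A reader might infer that the contrasts appear nowhere, or that active versus inactive cannot be estimated at all. The documents support neither: the gap is in the two analysis sections, and the pooled comparison is estimable as one contrast among days.
- **The zero depends on categorical day.** True, as step 2 shows. Categorical is the natural reading of an ANOVA factor running from Day 1 to Day 15, and the alternative codings stay confounded with time.
- **The Aim 1 reference may be settled.** Figure 1, which illustrates the three questions, is not available here and may show it. The text also leans towards Day 1, since that day standardizes exposure before abstinence and the aim concerns an abrupt switch. So it goes too far to say that the baseline is undefined. The procedures also use the word for each pain day's pre-cannabis test, but a before-and-after comparison around inactive cannabis would not test abstinence. What stays open in the visible text is mainly whether Day 1 is taken before or after cannabis.
- **The labels overlap, and the tests are the same.** The Overview's Day 9 vs Day 1 item includes tolerance being present, as does Aim 2(a), and the two-sided tests do not change. This stands for the p-values but not for the conclusions, which differ by label.
- **The order is inherent.** Abstinence must follow exposure, and reversal must follow abstinence. This stands: the fixed order is not itself a fault. The design label and the silence about time are.

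**Conclusion.** The point holds in this form and should be corrected before results are reported. Under the stated model, with day categorical, condition and its interaction contribute 0 df. Active versus inactive is 1 of 6 df on pain days and 1 of 14 over Days 1-15, confounded with order and time. The Aim 2 pairs exist in the protocol but not in either analysis section. Their labels are crossed against Aim 2, and the QST-TTS direction conflicts with the protocol's own account of that test. The Aim 1 reference is not named in the visible text, subject to Figure 1. Nothing visible supports randomized or crossover.

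A reader might go further and conclude that results are biased by a known amount, that choices were in fact made after seeing data, or that no randomization took place. The documents show none of these. They give no drift rate, they do not say when the comparisons were chosen, and they leave randomization undescribed rather than denied.

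**What to change.** 1. **Design label.** Describe a single fixed-sequence within-subject study and remove randomized and crossover, or describe the randomization if there was one. Reconcile the Risks text on cannabis administration with the Days 9-15 procedures, and the two counts of pain tests per day.
2. **Model and contrasts.** Replace condition and day with one within-subject day factor: 7 levels for pain, 15 for daily ratings. List Day 9 vs Day 1 as reversal after abstinence; Days 12 and 15 vs Day 9 as development, with a rule for the Overview's either-day wording; and Days 2, 5 and 8 vs Day 1 at a named time point as withdrawal hyperalgesia. Date any choice not already in the General Overview as made at the data-analysis stage.
3. **Labels and direction.** Correct the Overview's labels, and state the expected direction for QST-TTS separately from CPT latency.
4. **Outcome summary.** Name one summary over the six post-cannabis time points. Show raw pre- and post-cannabis values beside any change from the same-day pre-cannabis value, because Aim 1 itself expects the pre-cannabis level to shift. Ratings have a pre-cannabis value only on pain days, so a 15-day ratings model must use raw values.
5. **Confounding.** State that every between-day contrast is confounded with elapsed time and repeated pain testing. Report pooled active versus inactive as descriptive.

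The cost is wording and more cautious conclusions; no new data are needed. Change scores may lose or gain precision. As an illustration, take unit SDs, the sample-size section's correlation of 0.6 for every cross-day pair, and an assumed same-day correlation s. The variance of a raw day difference is 2(1 - 0.6) = 0.8, and that of a difference of changes is 4(1 - s). Changes are therefore less precise when s is below 0.8 and more precise above it. The documents give neither s nor the size of any pre-cannabis shift, which would also alter the effect being tested, so no power figure is offered.
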